Leveraging the Depression And Primary-care Partnership for Effectiveness-implementation Research (DAPPER) – will be initially randomized to 12 weekly one-hour sessions of IPT (3 months) or 6 months of fluoxetine (tapering up to 60mg). Those participants who are not in remission with at the conclusion of initial treatment will be re-randomized to second-line treatment (see below). Prior to randomization, participants will be given the option to receive their treatment at the health facility or by telephone.

Participants who are randomized to fluoxetine and conduct their visits by telephone will need to collect their medication at the health facility. If participants do not collect their medication at the health facility, fluoxetine may be delivered to participants in the community. A smaller, Part 2, of the study will consist of qualitative interviews and focus groups to assess the overall implementation strategy and gather feedback on the specific interventions. Please see "Part 2," below (and additional consent for this aspect of the study, attached).

Randomization and blinding: Randomization will take place after baseline measures are complete. Randomization will be done in blocks of 10 and stratified by sex and telephone vs in-person treatment to ensure that the treatment groups are approximately equal in size and in gender distribution and telephone vs in-person treatment. See below

for second randomization information. Clinical evaluators who conduct follow-up assessments will be blinded to treatment assignment. Participants, IPT therapists, fluoxetine providers cannot be blinded because they will either be providing or receiving the IPT and/or Fluoxetine treatment and therefore they will know their treatment status. In addition, at least one study coordinator will not be blinded to assist with tracking of participants.

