Retention: Based on previous work, retention is not expected to be a problem. Our pilot study of IPT for Sudanese refugees in Cairo had a 93% retention rate; our study of IPT for survivors of the Sichuan earthquake had an 85% retention rate and our ongoing study of integrated IPT care with HIV+GBV+ women in Kisumu has 300 enrollees with 20 dropouts (93% retention, to date). However, given uncertainty regarding generalizability to the KCH and other Kisumu County Ministry of Health facilities adult primary care clinics, the more conservative estimate of 20% drop-out will be used. However, provision of treatment over the telephone may improve retention rates. As part of retention efforts, participants will be asked to provide the name and phone number of a trusted adult who can be contacted if the study has concerns about participants' welfare or whereabouts. Therapists and fluoxetine providers will be asked to provide study cell phone numbers to study participants. Missed appointments will be followed with at least two efforts to reach the participant directly and/or through their contact (80% cell phone coverage). Likewise, at least two efforts will be made to reach drop-out participants for remaining measures.

Acute mental health care: IPT therapist and fluoxetine training will include risk assessment and referral procedures for acute mental health care needs. See Protection of Human Subjects section for details.

Clinical evaluators: Clinical evaluators will be blind to treatment group and will conduct baseline screening at the primary care clinic prior to initiating treatment, as well as re-assessments at months 1.5 (mid-treatment for IPT), 3 (mid-treatment for fluoxetine), 6, 9 month 12, 18, 24 and 30. Candidate clinical evaluators will undergo a two day training during which they will be introduced to the study measures and their proper application. At the conclusion of the training, the candidates will be observed in their administration of the measures, assessing for accuracy and completeness. If successful, they will be evaluated for reliability by conducting a group interview and comparing measure results. Those who demonstrate both accuracy and inter-rater reliability will be invited to join the study. Monetary compensation will be provided for completed measures at the local currency equivalent of 7usd.

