Data collection. Data collection will use tablets programmed with Research Electronic Data Capture (REDCap), similar to the electronic data system that we are currently using in Kisumu, Kenya (Online Data Kit [ODK]). REDCap now has an offline feature which does not require internet connectivity for data entry and can be later connected to the internet for upload to secure server.

Effectiveness outcomes

Clinical evaluators. Clinical evaluators will consent and screen study participants, complete baseline measures and then refer participants to (un-blinded) study coordinators for randomization. Blinded to group assignment, clinical evaluators will conduct 1.5 month (IPT treatment mid-point), 3 month (IPT end-of-treatment, fluoxetine-mid-treatment), and follow-up assessments. Candidate clinical evaluators will undergo a two day training during which they will be introduced to the study measures and their proper application. At the conclusion of the training, the candidates will be observed in their administration of the measures, assessing for accuracy and completeness. If successful, they will be evaluated for reliability by conducting a group interview and comparing measure results. Those who demonstrate both accuracy and inter-rater reliability will be invited to join the study. Monetary compensation will be provided for completed measures at the local currency equivalent of 7usd.

Data analysis plan

For *Hypothesis 1a* the analysis is standard intention to treat for 3 month (end of treatment) data. Our basic analysis strategy will be to fit logistic regression models for the outcome of MDD and/or PTSD remission, in this case with the predictor of group assignment (IPT or fluoxetine), demographics and severity of baseline depression and/or PTSD symptoms (BDI and PCL) . *Hypothesis 1b* will be analyzed for the sub-group of participants who are in remission from MDD and/or PTSD at months 1.5 or 1.5 and 3 and will use weighted generalized estimating equations logistic regression to accommodate the repeated measures on this subgroup through month 30.

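### With one stated block size of 10, unblinded coordinators randomising and no concealment step described, up to one in six first-stage allocations could be known in advance

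*Protocol*

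**What the plan says.** The protocol paragraph on randomization and blinding (under Study Procedures) gives the scheme for the first randomisation: "Randomization will be done in blocks of 10 and stratified by sex and telephone vs in-person treatment". The stated aim is "to ensure that the treatment groups are approximately equal in size and in gender distribution". The two factors make four strata. Sex is known beforehand, and participants choose telephone or in-person delivery before they are randomised. Facility is not a stratum.

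On who knows what, the same paragraph says "Participants, IPT therapists, fluoxetine providers cannot be blinded" and adds that "at least one study coordinator will not be blinded to assist with tracking of participants". The paragraph on clinical evaluators under Effectiveness outcomes says that evaluators "complete baseline measures and then refer participants to (un-blinded) study coordinators for randomization".

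Two features work as safeguards. Consent and screening are done by evaluators: "Clinical evaluators will consent and screen study participants". The other paragraph on evaluators, after the treatment schedule, says: "Clinical evaluators will be blind to treatment group and will conduct baseline screening at the primary care clinic". The order is also fixed: "Randomization will take place after baseline measures are complete".

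Neither document says how the sequence is generated, who holds it, or how the next assignment is hidden until it is used. REDCap is described for data capture and storage, not for allocation. The randomisation paragraph points forward for the second randomisation, but what follows names only the two options, switch and combination. It gives no block size, strata or concealment.

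**The concern.** In a blocked sequence the end of each block is fixed by what came before it. If the block size is a known constant and earlier allocations are visible, whoever randomises can sometimes know the next arm. Here the people who randomise are described as unblinded, the stratum is known beforehand, and one block size is written in the protocol.

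What is at stake is the order and timing of randomisation. The arms place different demands on participants: 12 weekly sessions for IPT against eight appointments over six months for fluoxetine. Hypothesis 3a itself expects travel time and cost to reduce the effect of IPT relative to fluoxetine. If someone expected to have trouble attending were held back until the coming arm suited them, the arms would differ in a way linked to outcome. The SAP model contains only time, group and their interaction. The protocol's Hypothesis 1a model adds demographics and baseline BDI and PCL. Neither could adjust for an unrecorded reason for delay.

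**Working it through.** The documents give no predictability figure, so there is nothing to reproduce first.

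**Inputs**
- Block size 10: protocol, randomization and blinding.
- Four strata, 2 (sex) × 2 (delivery mode): same paragraph.
- Ratio 1:1, so 5 + 5 per block: an assumption, inferred from the aim of approximately equal groups. No ratio is stated.
- 2,710 first-stage allocations: protocol, sample size calculations.
- Observer: knows the block size, where each block starts, and every earlier allocation in the stratum at all facilities.

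**Allocations that are certain.** An allocation is certain once one arm has used its five places. After k allocations in the block (k ≥ 5), the chance of this is 2 × C(5, k−5) / C(10, k).

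| Position | k | Calculation | Chance already certain |
|---|---|---|---|
| 1st to 5th | 0–4 | – | 0 |
| 6th | 5 | 2 × 1 / 252 | 0.8% |
| 7th | 6 | 2 × 5 / 210 | 4.8% |
| 8th | 7 | 2 × 10 / 120 | 16.7% |
| 9th | 8 | 2 × 10 / 45 | 44.4% |
| 10th | 9 | 2 × 5 / 10 | 100% |

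The sum is 0.0079 + 0.0476 + 0.1667 + 0.4444 + 1 = 1.667 per block, or 16.7%. This agrees with the closed form 1/(m+1) for a block of 2m: 1/(5+1) = 1/6. Enumerating all 252 balanced blocks gives the same answer. Over the first stage, 2,710 / 6 = 451.7, about 452.

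**Guessing.** An observer who always names the arm with more places left, and tosses a coin when they are equal, is right on average 5 + (1024/252 − 1)/2 = 6.53 times in 10. That is 65.3%, against 50% by chance.

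**Range.** The fully informed observer gives the upper end. An observer without the history within the stratum, or without the block size, has a lower share of certain allocations, possibly close to 0. Blocks are not specific to a facility, so someone who sees one facility's allocations falls between these ends. The documents do not allow that value to be fixed.

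**Effect of varying the sizes.** In a simulation of 100,000 allocations, the observer knew the full stratum history and the set of possible sizes. The share certain was 16.7% with a fixed 10, about 2.2% with sizes 4/6/8, and about 1.2% with sizes 8/10/12. Guessing was not scored for varying sizes. With fixed blocks of 8, 10 and 12 it is 66.6%, 65.3% and 64.3%, so it falls only slowly with block size. The gain shown here for varying the sizes is in certain allocations. Withholding the sizes and the sequence also counters guessing.

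**The case against.** The strongest reply is that the plan separates deciding who enters from allocating. Evaluators described as blind obtain consent, screen and take baseline measures, and randomisation comes afterwards. Foreknowledge would have to act through a coordinator's order or timing after baseline, or leak back to evaluators. This stands and lowers the risk considerably. It does not remove the risk, because blinded assessment is not the same as concealing the next allocation.

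A reader might infer that one allocation in six is in fact certain in advance, or that coordinators, providers and participants know all past allocations. The documents do not support either reading. Participants know their own treatment. Providers know their own cases, with caseloads capped at 10. At least one coordinator is unblinded, but nothing says that anyone sees the whole sequence across facilities.

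Three further points have force:
- Pausing and resuming enrolment (sample size calculations) is a rule about full caseloads, not discretion over individuals. Ability to attend is already an inclusion criterion. Both narrow the room for selection.
- The planned baseline covariates could absorb part of an imbalance in measured factors. Only the unmeasured part would be left.
- Among fixed sizes, 10 is less predictable than the smaller ones: by 1/(m+1), a block of 4 gives 33% and a block of 6 gives 25%.

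The SAP carries the same date as the protocol (27 October 2021) and is written in the past tense, so some or all allocations may already have been made.

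**Conclusion.** The point holds as an upper bound and as a design that can be improved cheaply. Under 1:1 allocation, at most about 1 in 6 first-stage allocations (about 452 of 2,710) could be known in advance, and up to 65.3% guessed. Both figures require a coordinator who knows the block size and tracks every allocation in each stratum across all facilities. For anyone with a partial view the figures are smaller, and the share certain may be close to zero.

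It would go too far to conclude that selection bias occurred or that the results are compromised. The documents show a route that is not closed off, not its use, and they allow no estimate of an effect on any outcome. The block-of-10 figures also cannot be carried over to the second randomisation, for which no block size is stated. There the gap is only that the method is not described, although the sample size is built on that stage.

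**What to change.** - **First-stage randomisations still to come:** replace the fixed block of 10 with permuted blocks whose sizes vary at random. Keep the sizes in a restricted document, out of the protocol and other site-facing papers.
- **Holding the list:** keep it in a system that shows one assignment at a time and that coordinators cannot view ahead. If REDCap is used, access needs care: the section on confidentiality of research data already gives study coordinators access to the participant key held there.
- **Second randomisation:** use the same method, and state its block scheme, strata and concealment.
- **Allocations already made:** report how the sequence was generated, who held it, and what concealment was used at each stage.

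The cost is a new allocation list and revised protocol wording, with no extra staff. The statistical price is a slightly larger possible imbalance within a stratum. If all randomisations are complete, only the reporting step applies.

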Study visits: To characterize the trajectory of symptom change during treatment, participants will be re-evaluated at the mid-point of treatment (month 1.5 for IPT and month 3 for fluoxetine). Treatment mid-point data is valuable because it can inform the minimum duration of treatment necessary to optimize mental health gains in a setting of scarce mental health resources. For example, if 90% of all observed treatment gains are achieved in the first half of treatment, subsequent implementation efforts might consider shortened courses of treatment. Participants will be assessed at month 3 (end of IPT treatment, mid-point of fluoxetine treatment) and at month 6 (end of fluoxetine treatment). For those participants who are in remission from depression and/or PTSD, follow up assessments will then continue at 9 month, 12 month and then at six month intervals until month 30 to assess for maintenance of gains and relapse. Assessments may be done at the health facility or by telephone. We are defining remission as absence of disease as defined by threshold criteria for Diagnostic and Statistical Manual of Mental Disorders-V (DSM-V) for PTSD and MDD. Those participants who have not yet remitted will be re-randomized to: switch of treatment (from IPT to fluoxetine or vice versa) or combination treatment (addition of IPT to fluoxetine or vice versa). See Figure 3.

Assessment schedule and rationale:

In order to characterize the trajectory of symptom change during treatment, participants will be re-evaluated at the mid-point of treatment (month 1.5 for IPT and month 3 for fluoxetine). Treatment mid-point data is valuable because it can inform the minimum duration of treatment necessary to optimize mental health gains in a setting of scarce mental health resources. For example, if 90% of all observed treatment gains are achieved by month 1.5, subsequent implementation efforts might consider shortened courses of treatment. Participants will be assessed at end of treatment (month 3 for IPT and month 6 for fluoxetine) and fluoxetine recipients will be tapered off the medication. At six months, participants will be re-assessed and then monitored at 6-month intervals until month 30 (Figure 3). Assessment visits may be done at the health facility or over the telephone.

Measures (Table 1): *Demographics.* We will obtain usual demographic measures, education, including individual income, assets, education and school fees, healthcare utilization, and time allocation.

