therapist (see therapist selection and training procedures, above), in 12 weekly 60-minute sessions. Participants randomized to receive fluoxetine will meet or speak with fluoxetine trained provider at baseline, 2 weeks, 4 weeks, 2, 3, 4, 5, and 6 months, for a total of eight appointments. Participants will be assessed for initiation of fluoxetine and advisement on common side effects. Fluoxetine participants will be started on 20mg (1 capsule per day) and will return for assessment of initial efficacy/tolerability at week 2. If the participant does not have any prohibitive side effects, dose will be maintained at 20mg (1 capsule). Participant will return for re-assessment at week 4, if the participant does not have any prohibitive side effects and does not have improvement on the Patient Health Questionnaire-2 (PHQ-2), dose will be increased to 40mg (2 capsule). At month 2, if the participant does not have any prohibitive side effects and does not have improvement on the PHQ-2, the dose will be increased to 60mg (3 capsule). Participants receiving treatment by telephone may be able to receive a 3 month supply at the minimum dose (20 mg per day). If the dose is increased during the intervening treatment visits, the participant will need to receive additional medication. Participants receiving treatment by telephone will be asked to pick up their medication within two days of their treatment call. If they do not collect their medication within 2 days, the medication will be delivered in the community. Studies support that higher fluoxetine doses do not show additional benefit.(Jakubovski, Varigonda, Freemantle, Taylor, & Bloch, 2016) See Protection of Human Subjects section for details on fluoxetine side effect management. The participant will be maintained at 20, 40 or 60 mg at the month 3, 4, and 5 visits, if the participant does not have any prohibitive side effects. At the month 6 visit, participants will be given instructions for tapering off fluoxetine, with decrease of the dose by 20mg

increments each week until reaching zero. Participants who were maintained on 20 mgs throughout the treatment period will have fluoxetine discontinued at the end of 6 months. IPT therapists and fluoxetine-trained providers will be compensated per IPT/medication session/day completed, at the local currency equivalent of 10usd.

Fluoxetine treatment duration: Participants treated with fluoxetine will be tapered off fluoxetine at month 6.

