As it pertains to antidepressants and psychotherapy, the evidence base comparing “switching” versus “combining” treatment for non-remitters (second line treatment) is still developing. However, the field does have meta-analytic data on the differences between treating depression with antidepressants or psychotherapy alone, versus their combination. A 2009 meta-analysis (n=2036) which compared combination treatment (psychotherapy and pharmacotherapy) to pharmacotherapy alone for depression found an effect size of 0.31 (Cohen’s d).²⁷ A 2007 meta-analysis (n=903) found that the remission rate for major depression treated with psychotherapy and pharmacotherapy was better than psychotherapy alone, with an odds ratio of 1.5928, which when converted to a Cohen’s d is 0.25.²⁹ While specific studies have not yet been completed for IPT and PTSD, we leveraged the above-referenced meta-analyses of the effects of general psychotherapy and general pharmacotherapy to estimate sample size for the proposed study. Based on those studies, we would need approximately 164 per treatment arm to compare combined psychotherapy-medication treatment with medication alone, and 242 to compare combined psychotherapy-medication with psychotherapy, alone (using a two-sided alpha of 0.05 and power of 0.80). Using the conservative estimate, we will need 242 for each of the four treatment arms (968, total) after the second randomization (switch to fluoxetine, switch to IPT, combination after fluoxetine, combination after IPT). Note, this strategy uses fluoxetine treatment for 6 months as a first line treatment,

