- (2) Acute suicidality (moderate or high score on the MINI suicidality module or Ask Suicidality-Screening Questionnaire (ASQ)) requiring higher level of care;
- (3) drug/alcohol use disorders requiring substance use treatment (AUDIT score of 8 or higher or DAST score of 3 or higher);
- (4) History of mania or requiring treatment for bipolar affective disorder hypomania (positive score on MINI mania/hypomania module or on the Mood Disorder Questionnaire (MDQ));

(5) Outside mental health treatment during the SMART-DAPPER treatment phases (any mental health treatment is allowed during follow-up phases and is recorded by study team). Participants will be asked to not start new mental health treatment during the SMART-DAPPER treatments, but will be assured that this is not prohibited. Participants who do will be treated as dropouts.

(6) Pregnant or breastfeeding

Recruitment

Working closely with clinic directors, providers and staff, we will integrate with the KCH and other Kisumu County Ministry of Health facilities primary care adult outpatient clinics. Waiting times for primary care medical outpatients at KCH and other Kisumu County Ministry of Health facilities can last many hours, creating an opportunity for study recruitment. As with our current study, we will provide health talks to waiting room attendees regarding emotional distress and the availability of treatment services for eligible participants through SMART-DAPPER, inviting interested individuals to meet with our study team in a private area for more information, consent and screening, as desired. A recruitment poster, brochure, and/or cards will be made available with key information about the study including the contact information to reach for further information. If individuals wish to undergo study screening while waiting for their appointment, we will work with the clinic to provide them with a card that will allow them to enter back in the waiting line without losing their place, or moving them to head of the line if their name was called during their time with our team. Prospective

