- If participants are not over the age of 18 years, they will be alerted to alternative mental health treatment options in the area.

Exclusion:

- Prospective participants who are identified as having cognitive dysfunction will be referred to primary care providers for work-up and treatment.

- Prospective participants with acute suicidality, will be escorted by our study team to the psychiatric facility for further evaluation and treatment.
- Prospective participants with substance use disorders with elevated scores on the AUDIT (8 or higher) or DAST (3 or higher) will be escorted by our study team to the nearest psychiatric facility for further evaluation and treatment.
- Prospective participants who have a history of mania or bipolar affective disorder will be screened for a current or past manic and hypomanic episode. If they have current symptoms, they will be escorted by our study team to the nearest psychiatric facility for further evaluation and treatment.
- Participants will be asked to not engage in mental health care outside the study during active treatment, but will be assured that they are not prohibited from doing this. They will also be told that they can use whatever type of mental health care they would like during the monitoring and follow-up phases of the study. They will be asked to alert study care provider and/or study coordinator if they begin receiving care outside the study and describe the type of care. If subjects do engage in outside mental health treatment during the SMART-DAPPER trial, they will be handled as a dropout at the point of engagement with the additional treatment.
- Pregnant and breastfeeding women will be excluded from the study given risk of fluoxetine in pregnancy and breastfeeding. These women will be invited to be screened for the study again after the conclusion of pregnancy and/or breastfeeding.

Adequacy of Protection against Risks

Recruitment and Consent Procedures:

Aim 1.

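### Non-remission is the only stated condition for the second randomisation, although three of its four arms contain fluoxetine and no visible text re-checks pregnancy after entry

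*Protocol*

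**What the plan says.** The rule for entering stage two appears twice in the protocol. Study Procedures has "Those participants who are not in remission with at the conclusion of initial treatment will be re-randomized to second-line treatment", and Study visits has "Those participants who have not yet remitted will be re-randomized to: switch of treatment (from IPT to fluoxetine or vice versa) or combination treatment". The SAP's closing paragraph likewise gives non-remission at the end of first-line treatment as the only criterion.

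Sample size calculations lists the four second-stage arms as "switch to fluoxetine, switch to IPT, combination after fluoxetine, combination after IPT".

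Exclusion criterion (6) reads "Pregnant or breastfeeding". The section on risks related to the inclusion and exclusion criteria gives the reason: "Pregnant and breastfeeding women will be excluded from the study given risk of fluoxetine in pregnancy and breastfeeding". It adds that these women may be screened again afterwards.

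At fluoxetine start, the treatment schedule section says "Participants will be assessed for initiation of fluoxetine and advisement on common side effects". Pregnancy is not named there, nor in the dosing steps, the side-effect rules, the assessment schedule or Table 1.

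**The concern.** The stated reason for the exclusion is a drug risk, so it matters whenever fluoxetine may be started, not only at entry. An IPT-first participant may first meet fluoxetine about three months after screening. If she conceives in that time and does not remit, the rule randomises her between switching to fluoxetine and adding fluoxetine, and neither is suitable for her. A fluoxetine-first woman who conceives and does not remit is randomised between IPT alone and IPT plus fluoxetine, and one of those is unsuitable.

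The main stake is participant safety. There is also a design consequence. The protocol states neither care nor analysis handling for a woman who has been randomised to an arm she cannot take, so such women would sit in the switch-versus-combination comparison without receiving their allocated treatment.

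**Working it through.** **Text check.** Set side by side, the second-stage options are:

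| First-line treatment | Switch | Combination | Options with fluoxetine |
|---|---|---|---|
| IPT | fluoxetine | IPT + fluoxetine | 2 of 2 |
| Fluoxetine | IPT | fluoxetine + IPT | 1 of 2 |

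The nearest safeguards in the visible protocol are:

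- The initiation assessment is generic, follows allocation and may be by telephone.
- Provider competency testing covers contraindications without naming pregnancy. The training text does single out bipolar disorder as something to rule out before starting the drug.
- The adherence audit covers eligibility, but it takes 10 charts a month from patients already treated.

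None of these names pregnancy or is a condition of the second randomisation.

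**The plan's own stage-two size.** Sample size calculations uses an odds ratio of 1.59 (printed as 1.5928, read here as 1.59 with a reference mark run on), two-sided alpha 0.05 and power 0.80.

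- d = ln(1.59) × √3/π = 0.2557.
- A two-sample t test needs 241.1 per arm, against the stated 242. The rounded d of 0.25 would need 252, so 242 reflects the unrounded conversion.
- 4 × 242 = 968, so 968/2 = 484 per first-line treatment.
- Upper case, if half of all 2710 enter with no earlier dropout: 2710 × 0.5 = 1355, or 677.5 per first-line treatment.

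**Women affected.** The documents give neither the share of women nor a conception rate. Assumed: 50-80% women, with 1-3% of them newly pregnant by month 3 and 2-6% by month 6.

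- IPT-first, all allocated fluoxetine: 484 × 0.5 × 0.01 = 2.4 to 484 × 0.8 × 0.03 = 11.6. With 677.5 the range is 3.4 to 16.3. The share is 0.5% to 2.4%.
- Fluoxetine-first, pregnant at month 6: 484 × 0.5 × 0.02 = 4.8 to 484 × 0.8 × 0.06 = 23.2, a share of 1.0% to 4.8%. With equal allocation, half of these (2.4 to 11.6) would draw combination.
- Not re-randomised if the check applies after both first-line treatments: 2.4 + 4.8 = about 7 to 11.6 + 23.2 = about 35 of 968, or 0.75% to 3.6%.

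A wider IPT-first assumption (50-90% women, 0.5-5% newly pregnant) gives 484 × 0.5 × 0.005 = 1.2 to 484 × 0.9 × 0.05 = 21.8.

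**Power cost of the fix** (d = 0.2557, two-sided alpha 0.05):

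| Loss | n per arm | Power |
|---|---|---|
| none | 242 | 0.801 |
| 2.4% (worst IPT-first) | 236.2 | 0.792 |
| 4.8% (worst fluoxetine-first) | 230.4 | 0.782 |

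**The case against.** The strongest reply is that this is an argument from silence. The visible text describes no pregnancy test or question at entry either, yet exclusion at entry is clearly intended, so silence at month 3 says little about practice. Eligibility is part of the fluoxetine treatment protocol that providers must follow without deviation, they are tested on contraindications, and they draw on a clinical guide that is not visible. Figure 3 and the appendices are not visible either.

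Much of this stands. It rules out a reading that someone might be tempted to take, namely that pregnant participants were or would be given fluoxetine. The documents show only where the rule would allocate them. It also means that two apparent supports carry little weight. Table 1 has no pregnancy item, but neither is an entry check described. Exclusion (5), on outside treatment, has on-study handling ("Participants who do will be treated as dropouts", and elsewhere "they will be handled as a dropout at the point of engagement with the additional treatment"), but that criterion is defined by conduct during treatment and needs such a rule by its nature. The contrast does not show that pregnancy was overlooked.

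What does not stand is that the generic safeguards answer the point. They act after allocation, when neither post-IPT option is usable.

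It may also be said that a pregnant fluoxetine-first non-remitter need not be barred, because switching to IPT is open to her. She can receive IPT, but she cannot properly be randomised when her other option contains fluoxetine.

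Finally, the SAP describes re-randomisation in the past tense. The documents do not establish how much of it remained when this protocol version was dated.

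**Conclusion.** The point holds as a defect in a stated rule and should be fixed. The rule omits the one exclusion that the protocol ties expressly to fluoxetine, and following it exactly sends a newly pregnant IPT-first non-remitter to a fluoxetine arm whichever option she draws. Confidence is medium, because a check may exist in material that is not visible.

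The size is small and rests wholly on assumed rates: about 2 to 12 women among 484 IPT-first non-remitters, or 3 to 16 among 677.5. How many would go on to take the drug cannot be estimated from the documents.

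Two limits apply. Breastfeeding shares the exclusion and the missing re-check, but it will rarely arise in women correctly screened as neither pregnant nor breastfeeding three or six months earlier. And a reader might infer that one check before re-randomisation closes the whole gap. It does not, because a woman who conceives while already taking fluoxetine, in either stage, is outside it.

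**What to change.** - Amend Study Procedures and Study visits so that only non-remitters who are not currently pregnant or breastfeeding are re-randomised, and align the SAP.
- Have unblinded staff record the check at the end-of-first-line visit (month 3 after IPT, month 6 after fluoxetine), after both first-line treatments and before the allocation is revealed. An unblinded study coordinator is already provided for under Randomization and blinding. The sponsor's clinicians should choose the method, including for telephone participants.
- Name the same check in the fluoxetine initiation assessment, for any start of the drug.
- Women who fail the check receive clinician-directed care, remain in follow-up and in the first-line intention-to-treat analysis, and are counted separately in the participant flow.
- State that switch versus combination is estimated in non-remitters eligible for both options.
- If Figure 3 or a separate procedure already contains the check, cite it in Study visits instead.

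The cost is a short amendment and one recorded item at an existing visit and at each fluoxetine start. On the assumptions above, 0.75% to 3.6% of non-remitters do not enter stage two, power falls from 0.801 to 0.782 at worst, and the second-stage result no longer applies to women who are pregnant at that point. Handling of conception during fluoxetine treatment needs its own statement.
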